The **working hypotheses** for this project are: **1)** recurrent hypoglycemia, like that seen in subjects with type 1 diabetes and iatrogenic hypoglycemia, will lead to an upregulation of glucose availability for the brain (by increased transport, and/or increased glycogen storage), thereby facilitating maintenance of cerebral metabolism during subsequent episodes of hypoglycemia, and **2)** recurrent hypoglycemia will lead to an increased GABA tone in hypothalamus, thereby suppressing glucose counterregulation during subsequent episodes of hypoglycemia. To address these hypotheses we will examine cerebral metabolism in subjects with type 1 diabetes and hypoglycemia unawareness, as well as in healthy volunteers preconditioned with euglycemia vs. recurrent hypoglycemia to induce HAAF, thereby permitting us to understand the clinical syndrome as well as isolate the effects of recurrent hypoglycemia from those induced by diabetes.

Aim 1: To determine the contribution of increased glucose availability in the brain to HAAF

Specific Aim 1a: To measure kinetic parameters for glucose transport and metabolism in the hypothalamus of subjects with type 1 diabetes and hypoglycemia unawareness and in healthy volunteers preconditioned with euglycemia vs. recurrent hypoglycemia to induce HAAF.

Hypothesis 1a.1: Subjects with type 1 diabetes and hypoglycemia unawareness will have a higher V_{\max} transport than will healthy volunteers preconditioned with euglycemia.

Hypothesis 1a.2: Healthy volunteers will have a higher V_{\max} transport following preconditioning with recurrent hypoglycemia than with euglycemia.

Specific Aim 1b: To measure brain glycogen turnover and content by ^{13}C MRS in healthy volunteers preconditioned with euglycemia vs. recurrent hypoglycemia to induce HAAF.

Hypothesis 1b: Subjects will have higher glycogen content following preconditioning with recurrent hypoglycemia than with euglycemia.

Aim 2: To determine the contribution of increased GABA tone in the hypothalamus to HAAF

Specific Aim 2: To measure euglycemic and hypoglycemic GABA levels in the hypothalamus of subjects with type 1 diabetes and HAAF and in healthy volunteers preconditioned with euglycemia vs. recurrent hypoglycemia to induce HAAF.

Hypothesis 2a: Hypothalamic GABA levels will be lower during hypoglycemia than during euglycemia in both normal controls and patients with type 1 diabetes.

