Regarding the second component of HAAF, the blunted counterregulatory hormonal response, recent investigations in rodents suggest a central role of an increased γ -aminobutyric acid (GABA) tone in the hypothalamus with recurrent hypoglycemia (16; 17). A fall in the hypothalamic levels of GABA, the main inhibitory neurotransmitter in the brain, appears necessary for activation of glucose counterregulatory responses during hypoglycemia. Recurrently hypoglycemic animals not only have elevated hypothalamic GABA levels, but they also fail to decrease these GABA levels in response to hypoglycemia (16). Furthermore, local application of glucose prevents this fall in a dose-dependent fashion, resulting in a positive correlation of extracellular glucose and GABA concentrations (17) and mechanistically linking increased glucose availability in this region to blunting of the GABA-regulated counterregulatory hormone release. With recently developed technology (14) (Appendix A, Preliminary studies) we can now test if the same sequence of events occurs in the human brain.

These prior data form the basis for our *working hypotheses* in the current application (Figure 1): In the healthy brain, a drop in plasma glucose results in a drop in brain glucose, as well as a reduction in glycogen (18) and GABA (see Preliminary studies). Following recurrent hypoglycemia, a drop in systemic glucose does not cause a similar drop in hypothalamic glucose levels due to upregulated transport capacity (V_{\max}^t), and thus the signal that leads to glycogen mobilization and a fall in hypoglycemic GABA levels is reduced, thereby blunting the hypoglycemia induced sympathoadrenal response. We will investigate these mechanisms both in healthy volunteers who have been preconditioned with recurrent hypoglycemia (a HAAF model), as well as in patients with type 1 diabetes, in order to distinguish the effects of HAAF alone from those of diabetes. With the elucidation of the contributions of glucose (Aim 1a), glycogen (Aim 1b) and GABA (Aim 2) to the pathogenesis of HAAF, new knowledge will be available that will permit the development of better strategies to prevent and treat this condition, such as pharmaceutical interventions to prevent an increase of hypothalamic GABA levels.

B. INNOVATION

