V_{max}^t will be compared between patients and euglycemia conditioned controls with a paired t-test; if data are highly skewed, non-parametric alternatives will be considered. Similar comparisons will be carried out, within the controls, between the results following euglycemic preconditioning and following hypoglycemic conditioning. Pilot data standard deviation in V_{max}^t (section C1.2) indicate that with 12 participants per group we have 85% power to detect paired-group differences of 14% in V_{max}^t with type I error of 5%. We have budgeted for 15 per group to allow for some failed scans without sacrificing power. Our previous data in the occipital cortex demonstrated ~17% higher glucose concentrations in subjects with type 1 diabetes and hypoglycemia unawareness vs. controls. Therefore, we expect to be able to detect a similar effect size in the hypothalamus in the proposed studies with 12 subjects in each group. While our power calculations are based on SD in V_{max}^t because we hypothesize that unidirectional glucose transport is upregulated in HAAF, our studies will also be able to reveal a change in V_{max}^{util} , if HAAF involves a change in glucose metabolism, thanks to the simultaneous measurement of these parameters with the new modeling approach.

Potential pitfalls and solutions:

Data will be collected as blood glucose is experimentally increased from 95 to 200, 300, or 400 mg/dl and we assume that the same kinetic constants will apply under hypoglycemia conditions. Under Aim 2, we will also obtain hypothalamic glucose data under hypoglycemia because we will be using the same MRS methods to obtain neurochemical profiles in these two aims. Since these data will also be available, we will assess the reliability of hypothalamic glucose measurements at hypoglycemia at a lower time resolution than that shown in Fig. 2B, e.g. in spectra acquired every 10-20 minutes instead of every 2.5 min. Because we save our MRS data in single shots, we can process these data to add over different time windows. Indeed, such lower time-

resolution data may also provide hypoglycemic glucose concentrations in hypothalamus. However, we chose to design the primary experiments under Aim 1a with hyperglycemic targets which we know will provide us with the kinetic parameters with certainty.

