Figure 8. Study protocol for healthy controls in Aim 2.

Euglycemia vs. hypoglycemia states: After preconditioning with euglycemia among the controls, GABA levels will be compared during euglycemia to during hypoglycemia with a repeated measures model with effects for glycemic state, acquisition time (5, 15, etc. minutes, Fig. 4), and their interaction. Correlation structures appropriate for doubly-repeated measures (across acquisition times within glycemic states, for two glycemic states) will be used. These comparisons will be repeated among the controls after preconditioning with hypoglycemia, and among the patients. Pilot work (Fig. 4) shows a standard deviation of the control group difference between euglycemic states and hypoglycemic states of 0.52 $\mu\text{mol/g}$, indicating that with 10 participants we have 85% power to detect paired-group differences of 0.53 $\mu\text{mol/g}$ with type I error of 5%. In the case that standard deviations are twice those observed in Figure 4, we have 85% power to detect differences of 1.10 $\mu\text{mol/g}$. Per-acquisition-time glycemic state comparisons will be adjusted for multiple comparisons using Sidak's method. We have budgeted for 12 participants to allow for two failed scans without sacrificing power. *Patients vs. controls:* Similar comparisons will be carried out between GABA levels in patient euglycemia states and in control euglycemia states after the controls are euglycemic preconditioned. This will be repeated for GABA in hypoglycemic states. Pilot work (Fig. 4) shows a standard deviation of the control group minus patient group difference during the hypoglycemic state of 0.25 $\mu\text{mol/g}$, indicating that with 10 participants we have 85% power to detect paired-group differences of 0.27 $\mu\text{mol/g}$ with type I error of 5%. In the case that standard deviations are twice those observed in Figure 4, we have 85% power to detect differences of 0.53 $\mu\text{mol/g}$. *Preconditioning:* Similar comparisons will be carried out between GABA levels during control euglycemia states for euglycemic preconditioning compared to hypoglycemic preconditioning. This will be repeated for GABA during hypoglycemic states.

Potential pitfalls and solutions:

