Prior rodent studies that demonstrated a role for increased hypothalamic GABA tone in blunting the counterregulatory response to hypoglycemia studied the VMH, while our spectroscopic voxel contains a larger portion of the hypothalamus. Despite this pitfall, our preliminary data demonstrate our ability to measure the hypothalamic GABA response to hypoglycemia both in controls and patients with type 1 diabetes. Therefore, we expect to be able to address our hypotheses regarding hypothalamic GABA despite these partial volume effects.

As discussed above, one potential problem we may encounter is that the protocol we use to induce HAAF will not be effective for all subjects enrolled in the study. To ensure that HAAF is present at the time we examine GABA metabolism, we will measure counterregulatory hormones in blood collected from subjects during hypoglycemia. If the epinephrine response (the hormone most blunted during most protocols in which HAAF is induced in humans) during the study done after hypoglycemic preconditioning is $\geq 70\%$ of the response measured during the study after euglycemic preconditioning, we will conclude that HAAF was not induced and the data will not be used for analysis. If HAAF fails to be induced in 1/3, 2/5, 3/7, 4/9,... of the studies (we will monitor in an ongoing way), we will change the protocol to induce HAAF to include more episodes of hypoglycemia before the GABA experiment. In addition, in this aim the blunted counterregulation will also be confirmed in patients with type 1 diabetes by comparing their hormone measurements during the hypoglycemic clamp to those of the euglycemia-preconditioned controls.

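### Whether patients differ beyond induced HAAF, the diabetes part of a stated objective, has no test or estimate in Aim 1a or Aim 2

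*Combined protocol and SAP*

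**What the plan says.** Specific Aims gives the purpose of having both populations: to "isolate the effects of recurrent hypoglycemia from those induced by diabetes". Section A (Significance) repeats it, saying both are studied "in order to distinguish the effects of HAAF alone from those of diabetes".

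The analysis plans in section C.2 contain two kinds of comparison between groups or preconditioning conditions:

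- **Aim 1a, patients against controls.** V_max transport "will be compared between patients and euglycemia conditioned controls with a paired t-test". Hypothesis 1a.1 matches: patients are expected to have a higher V_max "transport than will healthy volunteers preconditioned with euglycemia".
- **Aim 1a, within controls.** "Similar comparisons will be carried out, within the controls, between the results following euglycemic preconditioning and following hypoglycemic conditioning"
- **Aim 2, patients against controls.** "Similar comparisons will be carried out between GABA levels in patient euglycemia states and in control euglycemia states after the controls are euglycemic preconditioned", repeated for the hypoglycemic state.
- **Aim 2, within controls.** "GABA levels during control euglycemia states for euglycemic preconditioning compared to hypoglycemic preconditioning", again repeated for the hypoglycemic state.

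The Aim 2 hormone check in patients uses the same reference group, "comparing their hormone measurements during the hypoglycemic clamp to those of the euglycemia-preconditioned controls". No hypothesis, test, interval or power statement sets patients against hypoglycemia-preconditioned controls. There is no joint model of the three conditions and no rule for combining the two tests.

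**The concern.** Write P for the patient, E for the matched control after euglycemic preconditioning, and H for the same control after hypoglycemic preconditioning. P − E carries diabetes and HAAF together. H − E carries induced HAAF alone. What patients show beyond induced HAAF is P − H = (P − E) − (H − E), which the plan never forms.

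Without it, a reader has only two p-values. One significant and one not invites the conclusion that diabetes adds something; both significant invites the conclusion that it adds nothing. Neither follows, because a difference in significance is not a test of the difference.

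The documents come close to this kind of reasoning once. The Aim 1b rationale would set a positive glycogen result in volunteers against the investigators' previous observation of no increase in patients and attribute the discrepancy to diabetes. Aim 1b enrolls no patients, so the point cannot be repaired there, but it shows how the Aim 1a and Aim 2 results might be read.

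**Working it through.** **Inputs.** Aim 1a: 12 pairs, 85% power, type I error 5% (taken as two-sided; the plan does not say), detectable difference 14%. Pilot V_max transport in section C.1.2: 0.94 ± 0.21, so CV = 0.21/0.94 = 22.3%. Aim 2, patients against controls: 10 pairs, SD of the difference 0.25 μmol/g, detectable difference 0.27 μmol/g. The SD of P − H is given nowhere.

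**The plan's own figures.** For a paired t-test with n = 12, the standardized difference giving 85% power is 0.951 (noncentral t).

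- With the pilot CV as SD of the difference: 0.951 × 22.3% = 21.2%, not 14%. Power for 14% is then 51%.
- The stated 14% needs an SD of the difference of 14%/0.951 = 14.7%.
- Aim 2 with n = 10 and SD 0.25 gives 0.267, against the stated 0.27, so it reproduces.

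The failure of the 14% to follow from the pilot SD is a separate matter. Here 14.7% and 22.3% serve as a range for the unknown SD.

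**Reading two tests side by side.** Assume P − E, H − E and P − H have the same SD, s. Since Var(P − H) = 2s²(1 − r), setting this equal to s² gives r = 0.5 between the two planned differences. Simulated results for 12 matched sets, two-sided 5%:

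| True situation | Exactly one test significant | Only P − E significant | Both significant | Direct P − H significant |
|---|---|---|---|---|
| P = H, each test 85% power | 19% | about 10% | 76% | 5% |
| P = H, each test about 50% power | 35% | 17% | 33% | 5% |
| Patient effect twice the induced effect (85% power for the smaller) | 15% | 15% | 85% | 85% |

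The second row is roughly the case of a true 14% effect with an SD of 22.3%. For Aim 2 (n = 10, both effects 0.27, SD 0.25) the first two columns are 19% and 9%.

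**Precision of the missing contrast.** Half-width of the 95% CI = t × SD/√n, with t = 2.201 for 11 degrees of freedom:

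- SD 14.7%: 2.201 × 14.7/√12 = 9.3 percentage points.
- SD 22.3%: 2.201 × 22.3/√12 = 14.2 percentage points.

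For Aim 2, if P − H also had SD 0.25: 2.262 × 0.25/√10 = 0.18 μmol/g.

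**Power for P − H at n = 12.** A true 14% gap: 85% (SD 14.7%) or 51% (SD 22.3%). A 7% gap: 33% or 17%. As an illustration, take 17% in patients, borrowing the occipital glucose difference the plan cites, and 14% induced. The gap is 3% and power is about 10% or 7%. With 10 usable sets, power for a 14% gap falls to 76% or 43%.

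**The case against.** The strongest reply is that the main purpose is to see the effect of recurrent hypoglycemia free of diabetes. The Aim 1a rationale says what would support the mechanism: a rise in V_max transport in healthy people after induction. The within-control test answers that, and the planned group tests match hypotheses 1a.1, 1a.2, 2b and 2c. A reader might infer that the whole objective goes unanswered; the documents do not support that. What stands is narrower: the stated wish to tell HAAF from diabetes has a second half with no estimate.

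A reader might also infer that P − H would isolate diabetes. It would not. It compares chronic with briefly induced hypoglycemia. In Aim 1a, patients are scanned after a morning arrival on an insulin infusion, while controls are scanned in the afternoon without insulin after three clamps, and HAAF is not clamp-confirmed in patients. This objection stands and limits what the contrast can carry. P − E shares the patient-against-control differences in insulin, time of day and prior clamps.

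The 85% detection rate holds only if patients show twice the induced effect. For smaller gaps the contrast will often be inconclusive. Nor is every value guaranteed: data are dropped where the epinephrine response shows that HAAF was not induced, and the budget of 15 per group in Aim 1a allows for failed scans, not for this loss.

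Finally, the plan states no rule for Aims 1a and 2 that infers a diabetes effect from discordant tests. That is fair: the misreading is a risk left open, not a planned step.

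**Conclusion.** The concern holds for the diabetes component only. The planned tests remain valid for their own hypotheses, and induced HAAF has a direct test. Whether patients differ beyond induced HAAF has neither test nor estimate for V_max transport or GABA, although separating the two is a stated reason for the design.

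Relying on two p-values when the true effects are equal gives a discordant pair in about 19% of trials at 85% power and 35% at 50% power. About half of these point toward a diabetes effect, against 5% false positives in either direction for a direct test. These rates rest on two-sided 5% tests and equal SDs of the three differences, hence a correlation of 0.5; the documents give neither. The gap itself is a matter of what the plan contains and does not depend on them.

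**What to change.** Add to the Aim 1a and Aim 2 analysis plans, as a secondary analysis, the paired difference between patients and their matched hypoglycemia-preconditioned controls, with a 95% CI: V_max transport in Aim 1a, and GABA during euglycemia and during hypoglycemia in Aim 2. Use the matched sets in which HAAF was induced and report how many there are.

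State that no presence or absence of a diabetes effect will be inferred from one planned test being significant and the other not, or from both being significant.

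State the limits: the contrast is not a pure diabetes effect, for the reasons listed under the objection; precision is limited; and a wide interval leaves the question open.

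The cost is analysis-plan wording, with no new participants, scans or procedures. The downside is one more, imprecise comparison.

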Figure 2. A) Fit of the reversible Michaelis Menten model to steady state data from literature. **B)** Glucose concentrations obtained in the plasma and occipital cortex of one volunteer, together with the fit of the non-steady state, reversible Michaelis-Menten model to brain glucose concentrations.

kinetic parameters of cerebral glucose transport are traditionally obtained by fitting steady-state Michaelis-Menten models to steady-state brain glucose concentrations obtained as a function of plasma glucose concentrations. This way, K_M for transport (K_M^t) and the ratio of V_{\max} for transport (V_{\max}^t) to cerebral metabolic rate of glucose (CMR_{glc}) are obtained and, assuming a constant CMR_{glc} from prior work, V_{\max}^t is calculated (19; 20). Such steady-state measurements do not take advantage of the additional information available in dynamic data. The feasibility of determining all four kinetic parameters for cerebral transport and utilization (K_M^t , V_{\max}^t , K_M^{util} , V_{\max}^{util}) by fitting both dynamic and steady-state data was demonstrated recently for acetate (22). To apply the same approach to glucose transport and utilization, we measured brain and plasma glucose time courses during glucose infusions to raise and maintain plasma concentration at ~ 17 mmol/l for ~ 2 hours in 5 healthy volunteers. Occipital cortex glucose levels were measured from a 22-27mL voxel using previously described methods (12; 23) at 4 tesla. We fitted a reversible, non-steady-state Michaelis-Menten model to these data (Fig. 2B) (15) combined with steady-state plasma vs. brain glucose concentrations taken from literature (Fig. 2A) (19; 20). In addition to providing simultaneous measurements of glucose transport and utilization and obviating assumptions for constant CMR_{glc} , this methodology does not necessitate infusions of expensive or radioactive tracers. Using this new methodology, we found that the maximum transport capacity for glucose through the blood-brain barrier ($V_{\max}^t = 0.94 \pm 0.21$ $\mu\text{mol/g/min}$) was nearly two-fold higher than maximum cerebral glucose utilization ($V_{\max}^{util} = 0.48 \pm 0.12$ $\mu\text{mol/g/min}$). Furthermore, the glucose transport and utilization parameters were consistent with previously published values for the occipital cortex. These results were presented at a conference (15) and a manuscript describing them was submitted.

[figure not shown]

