nearby Analox machine to guide adjustments in the insulin infusion rate. The experiment will begin when the subject is at 95 mg/dl. At time 0, the intravenous insulin infusion will be fixed at 0.5 mU/kg/min, samples for blood glucose will be collected every 5 minutes and an intravenous infusion of glucose (20% dextrose) will be administered as necessary to maintain blood glucose at 95 mg/dl. At +5 minutes, subjects will be placed into the 7 tesla magnet (Fig. 5). Blood glucose will be maintained at 95 mg/dl during the next 25 minutes as the hypothalamic volume-of-interest (VOI) is selected and baseline MRS data are acquired. At +30 min, subjects will be given an intravenous bolus

injection of glucose over 1-2 minutes using the formula of administering 2 mg glucose/kg body weight for each 1 mg/dl increase desired that we have used with success previously (19). Immediately after the bolus injection, a continuous infusion of 20% dextrose will be started and the rate of administration will be adjusted to maintain the desired glucose target of 200 mg/dl, 300 mg/dl, or 400 mg/dl. MRS data will be collected continuously starting 10 minutes before the bolus injection (baseline) until the end of the study ~60 minutes after the bolus, which in our experience is sufficient to reach steady-state glucose concentrations in the brain and maintain them for at least 20 minutes (Fig. 2B). At the completion of the study, the infusions will be discontinued; the subject will resume their usual insulin regimen, and be fed a meal.

Healthy controls will be studied both after preconditioning with euglycemia and after preconditioning with recurrent hypoglycemia to induce HAAF, done in random order separated by a minimum of 6 weeks (Fig. 6). Female controls will have their two studies two months apart in order to control for phase of menstrual cycle. We will follow a hypoglycemia preconditioning protocol we (see preliminary data) and others (30; 31) have found to induce HAAF.

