¹³C-glycogen levels in the brain will be measured on a 4 T / 90 cm magnet (Oxford/Varian) using a quadrature 14 cm ¹H surface coil combined with a 9 cm diameter linear ¹³C coil (41). The [1-¹³C]glycogen NMR signal will be localized in a 7 × 5 × 6 cm³ voxel in the occipital lobe as described before (25). The amount of ¹³C label in the C1 position of glycogen will be quantified by the external reference method (23; 24). The [1-¹³C]glycogen concentrations will be divided by the plasma glucose isotopic enrichment (IE) to correct for differences in IEs between subjects and to determine the newly synthesized glycogen concentrations. ¹³C-glycogen levels will be corrected for the cerebrospinal fluid (CSF) content of the voxel (34).

Sample size justification and data analysis plan:

¹³C-glycogen levels will be compared following euglycemic preconditioning to following hypoglycemic conditioning with a repeated measures model with effects for precondition, acquisition time (5, 12, etc. hours), and their interaction; we will also test for an effect of the order of preconditioning. Correlation structures appropriate for doubly-repeated measures (across acquisition times within preconditioning, for two preconditioning sessions) will be used. Previous work (18) shows standard deviations of the group difference ranging from 0.2 to 0.4 μmol/g across the acquisition times, indicating that with 5 participants we will have 85% power to detect paired-group differences between 0.36 and 0.73 μmol/g with type I error of 5%. Per-acquisition-time group comparisons will be adjusted for multiple comparisons using Sidak's method. We have budgeted for 6 participants to allow for one failed study without sacrificing power. Since we have detected highly significant differences during and following single hypoglycemia vs. euglycemia in our prior studies with 5 subjects per group (18), we expect to be able to also detect a difference with 5 subjects who will serve as their own controls, if recurrent hypoglycemia does affect glycogen content/metabolism.

Potential pitfalls and solutions:

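### The control crossovers in Aims 1a and 2 randomise session order but analyse without a session (period) term; adding one, with blocked order, is a cheap gain in precision

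*Combined protocol and SAP*

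**What the plan says.** In section C.2, Aim 1a (Study Protocol), healthy controls are studied after euglycemic and after hypoglycemic preconditioning, "done in random order separated by a minimum of 6 weeks", with two months between studies for women. Aim 2 (Study Protocol) uses the same layout. No method for balancing the two orders is described.

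The Aim 1a analysis plan states that V_max for transport "will be compared between patients and euglycemia conditioned controls with a paired t-test", with non-parametric alternatives if the data are highly skewed. It then adds: "Similar comparisons will be carried out, within the controls, between the results following euglycemic preconditioning and following hypoglycemic conditioning". No order or session term appears.

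The Aim 2 plan specifies a repeated measures model with glycemic state, acquisition time and their interaction. For preconditioning it announces similar comparisons "between GABA levels during control euglycemia states for euglycemic preconditioning compared to hypoglycemic preconditioning", repeated for the hypoglycemic state. Again there is no order or session term.

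Aim 1b, which has the same crossover layout, does mention order: "we will also test for an effect of the order of preconditioning".

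**The concern.** Hypotheses 1a.2 and 2c are the within-person hypothalamic contrasts that separate the effect of recurrent hypoglycemia from that of diabetes. Each control contributes two sessions at least six weeks apart. Anything that differs between a first and a second visit, such as familiarity with the clamps or slow scanner drift, adds to the within-person difference in one order and subtracts from it in the other.

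An analysis without session treats that spread as random error. If the orders end up unequal, part of the shift also stays in the estimated effect. Unequal orders are plausible. No blocking is described, and data are lost after randomisation through failed scans ("We have budgeted for 15 per group to allow for some failed scans without sacrificing power") and through the rule, in both aims, that discards studies in which HAAF was not induced. At the budgeted 15 an exact split is impossible.

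**Working it through.** **The plan's own figure.** Aim 1a states 85% power for a 14% difference with 12 participants and 5% type I error. The pilot V_max for transport in C.1.2 is 0.94 with SD 0.21, so 14% is 0.14 × 0.94 = 0.132. If 0.21 is taken as the SD of the paired difference, two-sided power is 51%. The stated 85% needs an SD of the difference of about 0.138, which implies a within-pair correlation of 1 − 0.138²/(2 × 0.21²) ≈ 0.78 that the plan does not state. That is a separate matter. Everything below is in SD units of the within-person difference, starts from 85% power, and does not depend on it.

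**Model.** Let d be the hypoglycemic-minus-euglycemic difference for one control, δ the preconditioning effect, p the shift (session 2 minus session 1), and e the residual with SD 1. If euglycemic preconditioning came first (n1 controls), d = δ + p + e. If it came second (n2 controls), d = δ − p + e. The value of p is an assumption: 0, 0.25, 0.5 or 1.0. Tests are two-sided at 5%, also an assumption because sidedness is not stated.

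**Unadjusted paired test.** The mean of d has expectation δ + p(n1 − n2)/n. With equal orders the expected variance of d is 1 + p²n/(n − 1). At n = 12 this is 1.07, 1.27 and 2.09 for p = 0.25, 0.5 and 1.0.

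**Session-adjusted test.** The estimate is the equal-weight average of the two order-specific means of d. Its standard error is ½√(1/n1 + 1/n2), with n − 2 degrees of freedom, and p cancels. At 6:6 the standard error is 0.289, the same as 1/√12, so the only cost is the critical value (2.23 instead of 2.20).

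**Power with balanced orders.** The effect giving 85% power at zero shift is 0.95 SD at n = 12 and 1.07 SD at n = 10. Unadjusted figures are simulated.

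| Shift (SD) | n = 12 (6:6), unadjusted | n = 12, adjusted | n = 10 (5:5), unadjusted | n = 10, adjusted |
|---|---|---|---|---|
| 0 | 85% | 84% | 85% | 84% |
| 0.25 | 83% | 84% | 83% | 84% |
| 0.5 | 78% | 84% | 78% | 84% |
| 1.0 | 56% | 84% | 55% | 84% |

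At n = 12 the two analyses break even at a shift of about 0.16 SD. The unadjusted test is conservative when orders are balanced: actual alpha is about 3% at 0.5 SD and 0.6% at 1.0 SD.

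**Unequal orders.** The offset p(n1 − n2)/n is 0.17p at 7:5, 0.33p at 8:4 and 0.50p at 9:3 (n = 12), and 0.20p at 6:4 and 0.40p at 7:3 (n = 10). At 8:4 with a 0.5 SD shift, the unadjusted rejection rate is about 90% if the imbalance favours the effect and about 61% if it opposes it, against 80% adjusted. If simple randomisation were used (an assumption), the chance of 8:4 or worse at n = 12 would be 2 × (1 + 12 + 66 + 220 + 495)/4096 = 39%.

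**Cost of adjusting when there is no shift.** At 6:6 power goes from 85.0% to 84.3%. At 8:4 the standard error is ½√(1/8 + 1/4) = 0.306 and power is 80%, a loss of about 5 points.

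**The case against.** The best defence is that the main protection is already there. Order is randomised, so the unadjusted estimate is unbiased over the randomisation. The six-week minimum gives time for carryover to fade, and the two-month gap addresses menstrual phase. A paired analysis of such a design is valid, and with balanced orders an ignored shift makes it conservative. All of this stands, although neither gap removes a difference between first and second visits.

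The size is also uncertain. No passage reports a session shift. The 1.0 SD case assumes a shift larger than the 0.95 SD effect sought, and at 0.25 SD the loss is about one point. This too stands.

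Three stronger readings are tempting, and the documents support none of them:

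- A reader might infer that the planned results are biased. The offset exists only given an unequal realised split, and the documents report neither the split nor the randomisation method.
- A reader might infer that any shift costs power. With unequal orders a favourable shift can raise the rejection rate instead.
- A reader might apply the paired-test figures directly to Aim 2. Its planned analysis is a repeated measures model with doubly-repeated correlation structures, so the n = 10 figures show only the direction and rough size.

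**Conclusion.** The omission is real in both aims, and correcting it is a cheap improvement, not the repair of an invalid analysis. With balanced orders, the Aim 1a paired test at n = 12 loses about 6 points against the adjusted test at a 0.5 SD shift and about 28 points at 1.0 SD. Below about 0.16 SD it loses nothing. With unequal orders the estimate moves by the shift times (n1 − n2)/n. These sizes rest on assumed shifts, two-sided 5% tests and normal residuals.

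A reader might also infer that Aim 1b already holds the remedy. It may not. A main effect of order (sequence) compares participants' overall levels between the two orders. The session shift is the order-by-preconditioning contrast, so a test of order read as a main effect would leave the shift where it is.

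**What to change.** In the Aim 1a and Aim 2 analysis plans, pre-specify session (first or second) as a factor alongside preconditioning, with participant as the pairing unit. In Aim 2 this is one added term in the repeated measures model for the preconditioning comparison, in each glycemic state.

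For Aim 1a two equivalent forms exist:

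- average the mean hypoglycemic-minus-euglycemic difference over the two orders with equal weight, on n − 2 degrees of freedom; or
- compare the session-2-minus-session-1 differences between the two orders, whose mean difference is (p + δ) − (p − δ) = 2δ, and halve it.

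Comparing the hypoglycemic-minus-euglycemic differences between orders would be wrong: it gives (δ + p) − (δ − p) = 2p, the session shift, and cancels the effect. If the data are highly skewed, a rank-sum test on the session-2-minus-session-1 differences is the matching non-parametric choice. The plan should name the term as session or period and not reuse Aim 1b's order wording.

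Randomise order in blocks so that the split stays near equal. The cost is one degree of freedom. With no shift that is about 1 point of power when orders are balanced, rising to about 5 points at 8:4, which is why blocking should accompany the change.
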